- a) **Determine the effect of RA, compared with O₂, on maternal and fetal free radical activity.** We will test the *hypothesis* that RA, compared with O₂, for Category II EFM in labor will result in lower maternal and umbilical cord levels of malondialdehyde (MDA) and 4-hydroxynonenal (4-HNE), byproducts of free radical mediated lipid peroxidation and markers of oxidative stress that is associated with neonatal morbidity.
- b) **Investigate the effect of duration of RA or O₂ exposure on maternal free radical accumulation.** We will test the *hypothesis* that the magnitude of maternal free radical activity is directly related to duration of O₂ exposure by serially measuring maternal MDA and 4-HNE levels during labor.
- c) **Investigate the effect of O₂ exposure on placental oxidative stress.** We will test the hypothesis that intrapartum O₂ exposure is associated with increased local oxidative stress in the placenta, as represented by 4-HNE.

Secondary Aim 1 (Exploratory): Determine the impact of RA, compared with maternal O₂ supplementation, on neonatal outcomes in women with Category II EFM in labor. We will evaluate a composite outcome of neonatal morbidity including neonatal death, hypoxic-ischemic encephalopathy, seizures, hypothermia treatment, intubation, mechanical ventilation, and meconium aspiration syndrome in patients randomized to O₂ or RA in labor.

Secondary Aim 2: Determine the relationship between maternal serum and urine markers of oxidative stress during labor

[figure not shown]
The expected outcome of this proposal is high-quality mechanistic evidence for the pathophysiology of in-utero oxygen exposure. If RA is proven to be a more effective and safer option than O₂, it will change the clinical approach to intrauterine resuscitation of millions of women who labor and deliver each year in the U.S.

Background

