We propose a randomized controlled trial to investigate maternal and fetal free radical activity in laboring patients with Category II EFM exposed to O₂ or RA. A randomized controlled trial, the ‘gold-standard’ of study design, was chosen to produce high quality evidence on the safety of O₂ administration for Category II EFM. Our central hypothesis is that prolonged intrauterine exposure to O₂ during labor, compared with RA, generates free radicals that have downstream biochemical and clinical consequences to the neonate. This trial will be conducted on Labor and Delivery (L&D) at Washington University Medical Center (WUMC). Patients ≥37 weeks gestational age in active labor (≥6 centimeters cervical dilation) with Category II EFM necessitating intrauterine resuscitation (as determined by the care provider team) will be randomized to RA or maternal O₂ administration of 10L/min via nonrebreather face mask until delivery. All other resuscitation techniques (maternal repositioning, intravenous fluid bolus, etc) will be left to the discretion of the care provider team. EFM strips will be read and interpreted by the study nurse coordinator. Maternal blood, collected at randomization and within 1 hour post-delivery, placenta and umbilical artery blood collected at the time of delivery will be used to run MDA analyses. Maternal urine will be collection on enrollment (prior to rupture of membranes or cervical dilation <6cm), at time of randomization, and within 1 hour of delivery. At any of these time points, if patient has a foley catheter, the urine may be collected from the catheter. If patient does not have a catheter, either a straight catheterization can be performed or a clean catch sample can be obtained. The same commercially available assays used to quantify MDA and 4-HNE in our blood samples will be used for the urine samples.

Study staff will extract data from medical records including maternal demographics, antepartum history, intrapartum management, delivery outcomes, and neonatal outcomes. The patient’s primary nurse will perform real-time documentation of O₂ or RA initiation, any disruption in intervention, administration of amnioinfusion and additional resuscitation techniques performed (number of times patient is repositioned, total intravenous fluids, discontinuation of oxytocin).

Conduct of Trial

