1. Background, rationale, and hypothesis: Khaw et al demonstrated a dose response relationship between maternal MDA concentration and duration of O₂ exposure in a RCT of patients randomized to 60% O₂ by facemask or RA during scheduled cesareans [10]. In an analysis of 27 maternal MDA samples among patients randomized to O₂ in our pilot trial, we found higher median MDA levels in patients who received O₂ for 30-60 mins compared to those who received O₂ for <30 mins. This trend in maternal MDA, particularly in the first 60 minutes of O₂ exposure, suggests a dose-dependent relationship between

duration of O₂ exposure and maternal oxidative stress (unpublished, [name] et al). Here, we will test the hypothesis that duration of O₂ exposure correlates with levels of maternal MDA and 4-HNE.

2. Data collection: Study staff will draw maternal blood at time of randomization and within 1 hour of delivery. Because patients will be randomized to O₂ or RA when they have Category II EFM at any point after 6cm cervical dilation, durations of exposure will vary within groups. Since it is not feasible to sample the umbilical cord at multiple time points, this analysis will be restricted to maternal MDA and 4-HNE.
3. Outcome and data analysis: The primary outcome is mean maternal MDA and 4-HNE in O₂ exposed patients. We will compare mean MDA and 4-HNE across 5 pre-specified durations of O₂ exposure (<30 mins, 30-45 mins, 45-60 mins, 60-90 mins, or >90 minutes) using the one-way ANOVA test. If results of the ANOVA test suggests unequal means, the Tukey post hoc test will be used to identify the groups that differ. Linear regression will also be used to assess the effect of duration of exposure on MDA and 4-HNE concentrations.
4. Estimated statistical power: Maternal MDA differed significantly between 22 patients exposed to O₂ for <30 mins and 20 patients exposed to O₂ for 30-60 mins (unpublished, [name] et al). Based on these data we estimate that the sample size of 212 (106 in the O₂ group) will provide adequate power to detect differences between at least 2 of the 5 groups.

1. .

Secondary Aim 2: Determine the relationship between maternal serum and urine markers of oxidative stress during labor

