|--------------------------------|--|
| Maternal blood (serum) | -At randomization (active labor with Category II EFM) -Within 1 hour of delivery |
| Umbilical artery blood (serum) | -At delivery |
| Maternal urine | -On admission or at enrollment (prior to labor onset) -At randomization -Within 1 hour of delivery |

3. Outcome and data analysis: The primary outcome is MDA and 4-HNE urine concentrations. The primary outcome will be compared between room air and O₂ groups using Student's t test or Mann-Whitney *U* test, as appropriate. Linear regression will be performed to test the correlation between serum and urine concentrations. The mean MDA and 4-HNE urine concentrations throughout the three time points in labor (Table 3) will be graphed to assess baseline trends in oxidative stress over time within the room air group.
4. Estimated statistical power: Due to the exploratory nature of this aim, we will use a sample size of convenience and perform urine assessments in 100 patients (50 room air and 50 O₂). This aim will only include patients undergoing induction of labor, which comprises 70% of our cohort. These results will provide preliminary data regarding the feasibility of urinary oxidative stress analysis in labor and may allow for future oxidative stress studies to maximize patient participation by limiting invasive blood draws.

Safety Monitoring: The study team will review all neonatal adverse events and establish a data and safety monitoring board (DSMB), which will meet after 50% of participants have been recruited to review any adverse neonatal or maternal events among the study cohort and determine safety of continuing the study to completion. Reportable severe adverse neonatal outcomes include intrapartum stillbirth and neonatal death. Reportable non-severe adverse neonatal outcomes include need for hypothermia protocol, seizures, and prolonged NICU stay >72 hours. The study statistician will perform an interim analysis after 50% recruitment. The Haybittle-Peto stopping rule will be used in which a *p* <0.001 for the difference in the primary outcome between groups will guide further conduct of the trial.

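### Primary Aim (b) promises serial maternal sampling during labor, but blood is scheduled only at randomization and after delivery, and the duration analysis does not say which sample it uses

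*Combined protocol and SAP*

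**What the plan says.** Specific Aims, Primary Aim (b), is headed "Investigate the effect of duration of RA or O₂ exposure on maternal free radical accumulation". Its hypothesis is that maternal free radical activity rises with duration of O₂ exposure, to be tested "by serially measuring maternal MDA and 4-HNE levels during labor".

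The sampling statements are these:

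- Research Design and Methods, Overview: "Maternal blood, collected at randomization and within 1 hour post-delivery". Primary Aim 1, item 3, gives the same two times.
- Secondary Aim 1 of the design section (duration of exposure), item 2: "Study staff will draw maternal blood at time of randomization and within 1 hour of delivery".
- Table 2 repeats the two blood draws. For maternal urine it lists "On admission or at enrollment (prior to labor onset) -At randomization -Within 1 hour of delivery".
- The Overview describes the O₂ assignment as "maternal O₂ administration of 10L/min via nonrebreather face mask until delivery".

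Item 2 of the duration aim explains that "durations of exposure will vary within groups", because Category II tracings arise at different points in active labor. It restricts the aim to maternal markers because the cord cannot be sampled repeatedly. Item 3 then defines the outcome: "The primary outcome is mean maternal MDA and 4-HNE in O₂ exposed patients". Means are compared across five duration groups by one-way ANOVA, with Tukey comparisons if the ANOVA suggests unequal means, and linear regression on duration is added. Item 3 states no time point, change score, baseline covariate or RA comparison.

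**The concern.** The aim claims repeated measurement within labor, and the schedule does not contain it. A reader of the eventual report could take a difference between duration groups for a rise observed within women over time.

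The planned comparison is also not protected by randomization. Women were randomized to O₂ or RA, not to a length of exposure. If women with higher MDA at randomization go on to labor longer, or if MDA rises with labor whatever the mother breathes, the result looks like a dose-response to O₂. The section on the importance of the knowledge to be gained says the duration findings will inform later O₂ use, so the distinction matters to readers even though no decision rule in the trial depends on it.

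**Working it through.** **1. Schedule against aim.** Exposure starts at or after randomization and ends at delivery.

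| Maternal sample | Before exposure | During exposure | After delivery |
|---|---|---|---|
| Blood | at randomization | none | within 1 hour |
| Urine (induced women only) | admission or enrollment; randomization | none | within 1 hour |

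Each woman has a start value and an end value. That allows a before-after change but not a time course.

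**2. Which value is analysed.** Item 3 of the duration aim does not say. Primary Aim 1, item 4, places the trial's primary outcome at delivery, so delivery is the natural reading, but it is an inference. The covariate adjustment in Primary Aim 1, item 5, concerns the comparison between arms and does not name the randomization value.

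**3. The plan's own figure.** The duration aim gives no power figure and relies on the 106 O₂ women. That number reproduces from the UA MDA calculation: n per arm = 2(1.96 + 0.84)² × (2.0/0.83)² ≈ 91.1, rounded up to 92; 92 × 1.15 = 105.8, or 106 per arm and 212 in total.

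**4. Confounding by starting level.** Assume standardized variables, no true duration effect, and starting level as the only common cause. Let a be the correlation of the randomization value with the delivery value, and b its correlation with later duration. The documents give neither, so both are assumed. The spurious correlation of delivery value with duration is a × b. With n = 106, Fisher's transformation gives z = atanh(ab) × √103, and the false-positive rate is Φ(z − 1.96) + Φ(−z − 1.96). Simulation used 4,000 trials per setting.

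| a | b | ab | z | Regression, formula | Regression, simulated | Five-group ANOVA, simulated | Regression with randomization value |
|---|---|---|---|---|---|---|---|
| 0.3 | 0.1 | 0.03 | 0.30 | 6% | 6% | 6% | 5% |
| 0.5 | 0.2 | 0.10 | 1.02 | 17% | 16–18% | 10% | 5% |
| 0.7 | 0.3 | 0.21 | 2.16 | 58% | 59% | 33–34% | 5% |

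With b = 0 every method stays at about 5%. A separate run with skewed durations (median 52 minutes, a = 0.6, b = 0.2 to 0.4) gave 12–41% for ANOVA, 20–61% for regression and 4–5% after adjustment.

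The 5% in the last column assumes the starting value is measured without error. With reliability of 0.6 (assumed), the adjusted rate in the last row is about 17–19%.

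**5. Precision.** Take b = 0 and a true effect of 0.25 SD per SD of duration. Without the randomization value, z = 0.25 × √106 = 2.57 and power is Φ(2.57 − 1.96) ≈ 73% (simulated, about 70–71%). With it, the residual SD is √(1 − a²) = 0.954, 0.866 and 0.714 for a = 0.3, 0.5 and 0.7. Power is then about 77%, 84% and 95% by formula, and 75–93% across the range by simulation.

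**6. Confounding by elapsed labor.** In the O₂ arm, duration is close to time from randomization to delivery. Suppose markers rise 0.25 SD per SD of elapsed labor and O₂ does nothing. The model is the same as in step 5, so the delivery-only regression credits O₂ in about 70–71% of trials. Adding the randomization value raises this to 81–94% (a = 0.5 to 0.7), because it sharpens the estimate of a slope that is not due to O₂. Only women who labored without O₂ can separate the two.

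**7. Price of that separation.** With 106 women per arm and similar spread in elapsed time, the difference between two slopes has √2 times the standard error of one. A slope difference of 0.25 with the randomization value in the model gives z = 2.70/√2 = 1.91, 2.97/√2 = 2.10 and 3.60/√2 = 2.55. Power is about 48%, 56% and 72%.

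**The case against.** The strongest reply is that this is loose wording in one clause. The hypothesis is only that marker level is related to duration, and the duration aim restates it as a correlation. A between-woman association does address that, subject to confounding. The design section ranks the aim as secondary, and it drives neither the sample size nor the comparison between arms. All of this stands, and it limits the weight of the point.

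Three stronger readings are tempting, and the documents do not support them.

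- A reader might infer that the trial cannot show accumulation at all. It collects a start and an end value from each woman, so change in relation to duration can be analysed. What it cannot show is the course in between.
- A reader might infer that the plan commits to single post-delivery values. It states no time point; the gap is one of specification.
- A reader might take 59% as the expected error rate. It is the corner of an assumed range and applies to the regression. The first-named test, the ANOVA, reaches 34% there. Nothing in the documents shows that MDA at randomization predicts later duration, and if it does not, there is no inflation.

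It is also fair to object that baseline adjustment alone is an incomplete remedy. Step 6 bears this out, so the RA arm has to be part of the fix.

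**Conclusion.** The point holds in this form. The promise of serial measurement during labor contradicts every sampling statement in the protocol, and that part needs no assumption. As written, the duration analysis names neither its time point nor any use of the randomization sample. Read as the delivery value, it supports only an association between women that starting level and length of labor can confound.

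The size of any bias is unknown. The range of about 6–59% for regression and 6–34% for ANOVA is illustrative and rests wholly on assumed correlations. The gain in power from using the randomization value (about 70–71% to 75–93% in the setting of step 5) does not require confounding, but does depend on the assumed correlation between the two samples. The randomized comparison of O₂ with RA is untouched. This should be corrected, but it does not threaten the trial.

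**What to change.** 1. **Specific Aims, Primary Aim (b):** describe the aim as change in maternal MDA and 4-HNE from randomization to after delivery, in relation to exposure duration. Delete the reference to serial measurement during labor.
2. **Duration aim, item 3:** name the post-delivery value as the outcome. Regress it on continuous duration with the randomization value as a covariate. Record the times of both draws and of mask application, so that it is known whether the first sample preceded exposure.
3. **Same item:** fit the model with the RA arm included, using time from randomization to delivery, arm, their interaction and the randomization value. Aim (b) already names RA. The interaction asks whether the slope on elapsed time differs with O₂.
4. **Reporting:** present the result as an association, not as accumulation measured over time. This remains necessary after steps 2 and 3, because elapsed time is itself observed after randomization and the starting value is measured with error.

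**Cost:** both blood samples are already scheduled, and nurses already document when O₂ or RA starts, so the change is text plus a few recorded times. Women without a usable randomization sample drop out of this analysis. The interaction is estimated less precisely than a slope within one arm (step 7), so its confidence interval should be reported and a non-significant result not read as no effect.

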1. Background, rationale, and hypothesis: The majority of studies investigating MDA concentrations in the pregnant population have utilized serum or plasma samples.⁴⁸ In the non-pregnant population, urinary markers of oxidative stress have been proposed as an alternative to blood because they provide a less invasive way to assess oxidative status, can be used in large-scale studies, and may provide more accurate measurements of oxidative stress than blood because it is less liable to artificial increase of oxidative markers during sample collection and storage.⁴⁹ However, the effect of pregnancy physiology or labor on urine assessment of oxidative stress remains unknown. For example, glomerular filtration rate, renal plasma flow, proteinuria, and glucosuria increase in pregnancy⁵⁰. The effect of these changes in renal physiology on oxidative stress marker analysis is unknown. Furthermore, urine may reflect changes in oxidative stress that are less acute than changes detected in blood (i.e longer time to detect a difference). Given limited data on urine analysis of MDA and 4-HNE in pregnancy and especially during labor, I will study the relationship between MDA and 4-HNE concentrations in paired maternal serum and urine samples to test the hypothesis that urine can serve as a less invasive and readily available alternative to serum to quantify and trend oxidative stress in labor.

2. Data collection: Among patients enrolled in the RCT that are undergoing an induction of labor, urine samples will be collected by study staff at three time points. First, at the time of admission prior to the onset of labor in

order to obtain a baseline assessment of oxidative stress. Second, at the time of randomization in active labor which will be a paired specimen with maternal blood collected at the same time. Third, within 1 hour of delivery which will also be a paired specimen with maternal blood collected at the same time. Urine samples will be collected either as-mid void clean catch specimens or directly obtained from foley catheters in patients with epidurals. Table 2 outlines all planned sample collections in this trial. Urine samples will be centrifuged and stored at -80°C. The same commercially available assays used in Aims 1 and 2 will be used for MDA and 4-HNE quantification. Urine specific gravity will be measured in all samples to account for degree of urine dilution.

Table 2: Timing of all sample collection

| Sample | Time of collection |

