Anticipated challenges and safeguards: A potential limitation of the study is the inability to blind patients and healthcare providers to the allocation, however, the assessors will be blinded to allocation to limit bias in data analysis. Allocation concealment via use of opaque sealed envelopes will also limit selection bias. Bias could result from nurses and physicians managing subjects differently based on knowledge of their group assignment. To minimize this, providers will be specifically instructed to apply all other intrauterine resuscitation techniques as needed, irrespective of their group assignment. Any additional intrauterine resuscitation that is performed will be documented. To maximize adherence to protocol, we will conduct nursing and physician education sessions.

Protection of Human Subjects/Approvals

1. Risks to human subjects-

1A. Human subjects' involvement, characteristics, and design- The study will enroll 212 patients to investigate whether intrapartum O₂ administration in patients with Category II EFM is associated with oxidative stress. The study population will be English-speaking. Amongst the patients enrolled in the pilot trial, 77% were African American, 14% were Caucasian, 4% were Hispanic, and 5% were of other ethnicities. [name] and the other study members have completed the training module required by the WUSM Human Research Program Office and received education on the responsible conduct of research. The preceding pilot trial was approved by the IRB at WUSTL (IRB ID 201602164) and registered at ClinicalTrials.gov (ID NCT02741284).

1B. Sources of materials-

The study will involve collection of data from two key components:

- 1) Clinical Data Collection** from the medical records of mother and child. For all subjects, these data will be stored in a secure, password-protected REDCap database anonymized with study identifier only.
- 2) Maternal and cord blood samples**: All blood samples will be stored in a locked freezer that only the research team has access to. The maternal/ cord blood and placenta outcomes assessed in this study are additional materials collected for the purpose of the study and are not a part of routine prenatal care. Maternal and cord blood/placenta malondialdehyde levels are not used clinically and at present, cannot be directly linked to clinical outcomes. This will be disclosed to all study participants.

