1C. Potential Risks: The proposed study involves potentially rare risks to the subjects, including loss of confidential health information, provision of poor feedback to families regarding outcome data, physical risks of serial blood draws, and excessive demands on patients. We anticipate minimal risk to the neonate by "withholding" oxygen treatment for Category II EFM because (1) the clinical evidence thus far suggests that oxygen provides no benefit, and (2) there were no adverse outcomes amongst neonates in the room air group of my pilot trial. Protections against anticipated risks are outlined below under "Adequacy of Protection Against Risk."

2. Adequacy of protection against risks-

2A. Recruitment and Informed Consent: Pre-screening for eligibility criteria via medical record review will be conducted, and potential participants will be approached on Labor and Delivery. None of the data obtained in pre-screening will be saved. The study design, expectations, and risks/benefits will be explained, and potential subjects will be given a written informed consent form by a study team member. Consent will be documented by using a signed consent form. Trained study team members will have sufficient time to explain the study and the informed consent carefully in a private room, and eligible patients may decide to enroll at any time as long as they still meet eligibility criteria. Of note, our team has significant experience recruiting patients and neonates as part of prior investigations in this population.

2B. Protections Against Risk- Oxygen administration for Category II EFM is the current standard of practice. The safety of randomization to room air for Category II EFM has been demonstrated by the preceding pilot trial. All neonatal adverse events will be reviewed by the data and safety monitoring board (DSMB), which will meet after 50% of participants have been recruited to review any adverse neonatal or maternal events among the study cohort and determine safety of continuing the study to completion. The PI will be responsible for reporting all adverse events to the IRB.

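### The Overview permits straight catheterization for a research-only urine sample without first trying clean catch, a step the urine aim's own method does not list

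*Combined protocol and SAP*

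**What the plan says.** The Overview schedules maternal urine at enrollment, at randomization and within an hour after delivery. It first deals with women who already have a catheter: "At any of these time points, if patient has a foley catheter, the urine may be collected from the catheter". For the others, "either a straight catheterization can be performed or a clean catch sample can be obtained". It states no preference between the two methods and requires neither a clinical indication nor a failed clean catch.

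Secondary Aim 2, item 2 (Data collection), gives the detailed method: "Urine samples will be collected either as-mid void clean catch specimens or directly obtained from foley catheters in patients with epidurals". Straight catheterization is not listed. Item 1 of the same aim sets out to test whether "urine can serve as a less invasive and readily available alternative to serum". Item 3 states that "The primary outcome is MDA and 4-HNE urine concentrations". Item 4 calls the aim exploratory: "we will use a sample size of convenience and perform urine assessments in 100 patients", split 50 and 50 between the arms and limited to women undergoing induction.

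Under Protection of Human Subjects, 1B says that the maternal and "cord blood and placenta outcomes assessed in this study are additional materials collected for the purpose of the study". Section 1C lists, among other risks, "physical risks of serial blood draws, and excessive demands on patients". The sampling protections in 2B deal with blood draws, cord blood and placenta. Separately, the Informed Consent paragraph in 2B promises a consent document that describes all study procedures and their possible risks.

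**The concern.** Straight catheterization is an invasive step. Here it may be used to obtain a sample with no stated clinical purpose, even when the woman could simply have voided. That sits badly with an aim whose rationale is that urine spares women invasive sampling. The protocol's own text on materials, risks and protections does not name the step.

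At stake are participant burden and safety in an exploratory sub-study, and clarity for staff who must decide which instruction to follow. The randomized comparison of maternal and umbilical artery markers does not depend on urine.

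**Working it through.** This is a comparison of texts. Secondary Aim 2 sets no detectable difference and no power target, so no power calculation would measure the problem.

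**1. Is the sample research-only?** The Overview sends the urine for MDA and 4-HNE assay. Secondary Aim 2 adds specific gravity, solely to allow for dilution. The blood-draw paragraph in 2B says that MDA results have no clinical use. No clinical use of the urine is stated anywhere. Research-only is therefore an inference, but a sound one.

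**2. Which methods does each section allow?**

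| Situation | Overview | Secondary Aim 2, item 2 |
|---|---|---|
| Foley in place | May use it | May use it (tied to epidurals) |
| No catheter, clean catch | Allowed | Allowed |
| No catheter, straight catheterization | Allowed, no condition | Not listed |

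Staff who use an existing Foley or a clean catch comply with both sections. The difference is one of breadth: the Overview adds one invasive option.

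**3. At which time points?** The Overview introduces the catheter rules as applying at any of the three collections, and the sentence on women without a catheter follows directly. The natural reading is that straight catheterization is open at all three. The first sample comes before labor onset according to Secondary Aim 2, so only the second and third concern a woman in labor or just delivered.

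**4. Do the human-subjects sections name it?** Section 1B covers clinical data, maternal and cord blood, and placenta. The only physical sampling risk named in 1C is that of blood draws. The sampling protections in 2B cover blood, cord and placenta. Neither urine collection nor catheterization is named in this part of the protocol. The consent paragraph in 2B reaches them only through its general commitment.

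**5. Scale.** The 100 urine patients at three time points give 100 × 3 = 300 collections. The first sample precedes randomization, and Primary Aim 1 (feasibility of the sample size) reports that 40% of enrolled pilot patients met the criteria for randomization. Suppose that rate held among induced women and each gave a baseline sample. Then 100 randomized women would require 100 / 0.40 = 250 baseline collections, and 250 + 100 + 100 = 450 in all. These figures count collections, not catheterizations. The documents give neither the share of women with a Foley nor the success rate of clean catch, so the number of straight catheterizations cannot be estimated.

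**The case against.** The strongest reply has three parts.

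*The wording is permissive, and consent covers it.* The Overview neither requires nor prefers catheterization, the narrower rule is in the detailed method, and 2B commits the team to describing every procedure and risk. This stands to a large extent. A reader might infer that the two sections contradict each other, or that women would be catheterized without being told. The documents support neither inference. One course of action satisfies both sections, the consent form is not in the file, the consent commitment is general, and the list in 1C is worded as non-exhaustive. What remains is that the Overview authorizes the step without condition and that 1B, 1C and 2B do not name it. The omission from those sections would by itself be only missing detail.

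*A catheter sample may be cleaner.* In active labor and after delivery, voided urine could contain blood or amniotic fluid, which matters for an oxidative-marker assay. This is plausible, but the protocol does not give it as a reason, and Secondary Aim 2 already accepts clean catch at all three time points. It does show that the fallback must cover an unusable sample as well as inability to void.

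*The consequence is small.* It requires a woman with no Foley who could give a clean catch and whose staff choose a catheter anyway. That is correct, and it limits the grade. A reader might also infer a threat to the trial's power or conclusions. None follows, because urine enters only an exploratory aim.

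**Conclusion.** The point holds as a cheap improvement in participant safety and burden, graded minor. The Overview permits an avoidable invasive procedure that the urine aim's own method does not list and that runs against the aim's rationale.

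The conclusion rests on two readings: that the urine has no clinical use, since none is stated, and that the rule for women without a catheter applies at all three time points. It does not depend on any assumed frequency of catheterization. It makes no claim of inadequate consent, and it leaves the primary outcome, sample size and main conclusions as they are.

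**What to change.** Amend the Overview to match Secondary Aim 2:

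- Use an existing Foley if there is one; otherwise use clean catch.
- Allow straight catheterization for the study only when the woman cannot void or the voided sample is unusable (for example, visibly contaminated with blood or amniotic fluid), and she agrees at that time.
- Allow urine to be taken from a catheterization done for clinical reasons.
- Record the collection method for every sample.
- Carry the same rule into Secondary Aim 2, item 2, and name urine collection and catheterization, with their risks and protections, in 1B, 1C and 2B.

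The cost is protocol wording, one extra data item, and possibly a few exploratory samples lost or contaminated. Removing the option altogether would be simpler but less good. The missing samples would come only from women with no Foley and no usable clean catch and, since Secondary Aim 2 ties Foleys to epidurals, the loss would be selective.
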